10.4.4.2 Primary Efficacy Endpoint

The primary endpoint is the change from Baseline to Week 4 in the PANSS total score. The null and alternative hypothesis for each dose level are as follows:

H₀: the difference in the change from Baseline to Week 4 in the PANSS total score between LB-102 active treatment and placebo is equal to 0;

H₁: the difference in the change from Baseline to Week 4 in the PANSS total score between LB-102 active treatment and placebo is different from 0.

All efficacy endpoints will be analyzed for the mITT Analysis Set, and the primary endpoint will also be analyzed for the PP Analysis Set.

Principal Analysis

In line with the estimand definition, all data collected after the occurrence of an ICE will be included in the primary efficacy analysis. As a primary analysis, all missing data due to study discontinuation for lack of efficacy or drug-related AEs will be imputed assuming a Missing Not At Random (MNAR) mechanism and assuming that after withdrawal the subjects revert to the distribution of the worst PANSS score values observed up to time of discontinuation, whereas missing data due to discontinuation for any other reason, will be imputed under a Missing At Random (MAR) assumption using a Multiple Imputation (MI) approach.

The primary efficacy endpoint (change from Baseline to Week 4 on the PANSS total score) will be analyzed using a Mixed Model for Repeated Measures (MMRM) approach, including site, visit, treatment, and their interaction as categorical covariates and Baseline PANSS as continuous covariates. Within -patient correlation across repeated measures will be accounted for by using an unstructured correlation, or the best fit structure should an unstructured matrix cause convergence issues. The differences between active treatment groups and placebo at Week 4 will be estimated alongside confidence intervals (CIs) and *P* values. The model will be fit separately for each imputed dataset and results pooled using Rubin's rules to derive one treatment effect estimate.

This analysis will be performed for the mITT and repeated for the PP Analysis Set. Should the mITT and ITT differ substantially (e.g., by at least 10%) the primary analysis will be performed for the ITT and the mITT only be regarded as supportive information.

Confidential Page 82 of 102

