## 2.3 Estimands

The primary study estimand is described in Table 1 below.

**Table 1.** Primary Study Estimand: PANSS Total Score at Week 4

Objective: To determine whether LB-102 [REDACTED] administered to patients with acutely exacerbated schizophrenia demonstrates antipsychotic efficacy as determined by a change from Baseline on the PANSS total score, compared to placebo	
Estimand: Treatment effect of LB-102 vs Placebo regardless of intercurrent events (treatment-policy)	
Treatment: LB-102 (50 mg or 75 mg) and matching Placebo	
ESTIMAND	ANALYSIS
Target population	Analysis set
Adult patients with acute schizophrenia as identified by the study eligibility criteria	Intent-to-Treat (ITT) analysis set, defined as all randomized patients.  Should the ITT and modified ITT (mITT) analysis sets overlap substantially (i.e. 95% of patients in the former are also in the latter), the mITT will be considered as the reference analysis set for all estimand-related analyses.
Variable	Outcome measure
PANSS Total Score at Week 4	Change from Baseline to Week 4 in the PANSS total score
Handling of intercurrent events	Handling of missing data

 
• Taking a prohibited medication prior to Week 4
 
• Starting an emergency treatment prior to Week 4
 
 
All of these intercurrent events (ICEs) will be handled via a treatment-policy strategy, i.e. data collected after their occurrence will be included in the statistical analysis of the endpoint.
	
All missing data due to study discontinuation for lack of efficacy or drug-related adverse events (AEs) will be imputed assuming a Missing Not at Random (MNAR) mechanism and assuming that after withdrawal the patients revert to the distribution of the worst PANSS score values observed up to time of discontinuation, whereas missing data due to discontinuation for any other reason, will be imputed under a Missing at Random (MAR) assumption using a Multiple Imputation (MI) approach.
 
As a sensitivity analysis, missing data that was imputed under a MAR mechanism in the primary analysis will be imputed under a MNAR mechanism using a tipping-point approach to check robustness of the main analysis

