### **5.11.2 Primary Efficacy Analysis**

In line with the primary study estimand, prior to performing the statistical modelling missing data due to a discontinuation related to either lack of efficacy or drug-related AEs will be imputed assuming a MNAR mechanism whereas missing data due to discontinuation for any other reason or non-monotone missing data will be imputed under a MAR mechanism.

The MAR imputation will use a fully conditional specification approach with a predictive mean matching (PMM) method, where a missing value is imputed using a value randomly selected from a set of  $k$  ( $= 5$ ) observed values that are the closest to the predicted value for the missing data point. This imputation will be performed using the following SAS code:

```

proc mi data =  n impute = 100 seed = 99 out = impute01 minimum
= 30 maximum = 210 round = 1;
  by trt01p;
  var baseline week_1 week_2 week_3 week_4;
  fcs nbiter = 1000 regpmm( baseline);
  fcs nbiter = 1000 regpmm(week_1 = baseline);
  fcs nbiter = 1000 regpmm(week_2 = baseline week_1);
  fcs nbiter = 1000 regpmm(week_3 = baseline week_1 week_2);
  fcs nbiter = 1000 regpmm(week_4 = baseline week_1 week_3);
run;

```

Missing values for patients dropping out from the study because of lack of efficacy or drug-related AEs will be imputed iteratively assuming that after withdrawal the patients will follow the distribution of the worst values observed up to the study visit at which they withdraw. A schematic illustration of the process would be as follows:

- All patients with non-missing Week 1 PANSS score values (including both those with an actual observed Week 1 value and those who had this value imputed as part of the MAR imputation step described above) will have a variable (WORST1) calculated which is the maximum PANSS score values observed between baseline and Week 1, whereas those with a missing Week 1 value will have a missing value for WORST1 as well
- The imputation step will use WORST1 as the variable to be imputed and baseline and Week 1 values as predictors using the PMM method described above for the MAR imputation step. Patients with a missing Week 1 value will thus have their Week 1 value imputed by the WORST1 value predicted by the imputation procedure.

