- A similar approach will thus be followed for Week 2, i.e. creating a WORST2 variable, imputing it using a PMM approach and using this imputed value as the Week 2 value for patients with a missing assessment at that visit.
- This approach will then be repeated for Week 3 and 4, until at last all values missing because of lack of efficacy or drug-related AEs have been imputed/replaced.

The below sample SAS code implements the above steps, with the input dataset of the first DATA STEP being the output dataset of the PROC MI step above and including the patient ID and the MAR-imputed PANSS data in wide format, one column for timepoint, i.e. baseline, Week 1, 2, 3 and 4:

```

* Create WORST1 variable;

data step1;
  set analysis02;
  if not missing(week_1) then worst1 = max(baseline, week_1);
run;

* Impute WORST1 for patients with missing Week 1 data;

```

```

proc mi data = step1 nimpute = 1 seed = 99 out = step2a minimum = 30 maximum
= 210;
  by _imputation;
  var baseline worst1;
  fcs nbiter = 1000 regpmm(worst1 = baseline);
run;

* Set Week 1 = WORST1 for missing data and create WORST2 variable;

data step2b;
  set step2a;
  week_1 = ifn(missing(week_1), worst1, week_1);
  if not missing(week_2) then worst2 = max(baseline, week_1, week_2);
run;

* Impute WORST2 for patients with missing Week 2 data;

proc mi data = step2b nimpute = 1 seed = 99 out = step3a minimum = 30 maximum
= 210;
  by _imputation;
  var baseline week_1 worst2;
  fcs nbiter = 1000 regpmm(worst2 = baseline week_1);
run;

* Set Week 2 = WORST2 for missing data and create WORST3 variable;

data step3b;
  set step3a;
  week_2 = ifn(missing(week_2), worst2, week_2);
  if not missing(week_3) then worst3 = max(baseline, week_1, week_2, week_3);
run;

* Impute WORST3 for patients with missing Week 3 data;

proc mi data = step3b nimpute = 1 seed = 99 out = step4a minimum = 30 maximum
= 210;
  var baseline week_1 week_2 worst3;
  fcs nbiter = 1000 regpmm(worst3 = baseline week_1 week_2);
run;

* Set Week 3 = WORST3 for missing data and create WORST4 variable;

data step4b;
  set step4a;
  week_3 = ifn(missing(week_3), worst3, week_3);
  if not missing(week_4) then worst4 = max(baseline, week_1, week_2, week_3,
week_4);
run;

* Impute WORST4 for patients with missing Week 4 data;

proc mi data = step4b nimpute = 1 seed = 99 out = step5a minimum = 30 maximum
= 210;

```

```

var baseline week_1 week_2 week_3 worst4;
fcs nbiter = 1000 regpmm(worst4 = baseline week_1 week_2 week_3);
run;

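### Worst-value imputation: the SAP's steps and code extend the worst-score horizon to Week 4, while the stated rule stops it at withdrawal

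*SAP*

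**What the plan says.** Three places state the rule. SAP 5.11.2 assumes that "after withdrawal the patients will follow the distribution of the worst values observed up to the study visit at which they withdraw". SAP Table 1 (section 2.3) assumes that "after withdrawal the patients revert to the distribution of the worst PANSS score values observed up to time of discontinuation". Protocol 10.4.4.2 has it that "the subjects revert to the distribution of the worst PANSS score values observed up to time of discontinuation". The rule covers only scores missing after discontinuation for lack of efficacy or a drug-related adverse event (failures, below). Other missing scores are imputed under MAR.

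SAP 5.11.2 then gives the procedure in bullets and sample code. WORST1 is the highest PANSS total over Baseline and Week 1. It is imputed by predictive mean matching where Week 1 is missing, and the result is written in as the Week 1 score. Week 2 is handled the same way with WORST2, which covers Baseline to Week 2: "week_2 = ifn(missing(week_2), worst2, week_2". The bullets continue: "This approach will then be repeated for Week 3 and 4". In the last step the code reads "if not missing(week_4) then worst4 = max(baseline, week_1, week_2, week_3" and adds Week 4 to the maximum. Any Week 4 score still missing is set to the imputed WORST4.

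**The concern.** The rule ties the horizon to each patient's withdrawal, but the procedure contains no withdrawal visit. A patient who left after Week 1 is scored at the primary timepoint from other patients' worst scores over four weeks, three of which fall after that patient had gone. Imputed worst values are also written back as visit scores and used as predictors in the next step.

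These values enter the primary Week 4 comparison. A programmer working from Table 1 and one working from the sample code would build different Week 4 data, and the reported estimate would not be the one that Table 1 describes.

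**Working it through.** **1. The plan's own figures.** Neither document gives a figure for the imputation. The yardstick is the design in SAP section 3: a difference of 8 points, SD 18, 25% drop-out. The numbers randomized are redacted, so the 85% power can be neither confirmed nor refuted here, and the point does not depend on it.

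**2. Rule against procedure.** Write B for Baseline and W1 to W4 for the visit scores.

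| First missing visit | Horizon frozen at that visit | Source of Week 4 in the SAP code |
|---|---|---|
| Week 1 | max(B, W1) | max(B, W1, W2, W3, W4) |
| Week 2 | max(B, W1, W2) | max(B, W1, W2, W3, W4) |
| Week 3 | max(B, W1, W2, W3) | max(B, W1, W2, W3, W4) |
| Week 4 | max(B, W1, W2, W3, W4) | the same |

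**3. Direction.** For any donor, WORST(k+1) = max(WORSTk, W(k+1)) ≥ WORSTk. The variable being imputed can therefore only rise as the horizon lengthens. In addition, the matching model is fitted on donors' actual visit scores, while a failure supplies an already imputed maximum as the predictor.

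**4. Size.** The WORST1 to WORST4 chain was simulated (matching on 5 donors, no treatment term) and compared with a version that keeps the value drawn at the first missing visit.
- From the documents: SD 18 at Week 4, 3:3:3:1 allocation, baseline PANSS 80 to 120, an 8-point difference.
- Assumed: 108/108/108/36 patients; 12.5% failures per arm (10 to 25% also tried); visit SDs 9/13/16/18; baseline mean 95 and SD 9; ANCOVA at Week 4 in place of the MMRM.
- Grid of 27 settings: three improvement patterns (placebo Week 4 change −15, −7 or −2) × correlation 0.7, 0.8 or 0.9 × lack-of-efficacy share of failures 0, 50 or 100%; 150 trials each.

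The mean excess in imputed Week 4 PANSS for failures was 0.5 to 6.7 points and was positive in all 27 settings. By first missing visit:
- Week 1: 2.6 to 12.6
- Week 2: 0.0 to 8.8
- Week 3: −0.1 to 5.1
- Week 4: 0

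A second simulation (20 to 28% drop-out) gave 3.0 to 4.6 points overall. Its base case shows the pattern by last observed visit, as mean imputed Week 4 change:

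| Last observed | SAP steps | Frozen | Gap |
|---|---|---|---|
| None post-baseline | 8.8 | 1.4 | 7.4 |
| Week 1 | 8.7 | 4.3 | 4.4 |
| Week 2 | 8.8 | 6.5 | 2.3 |
| Week 3 | 8.8 | 8.8 | 0 |

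**5. Treatment contrast (active minus placebo).** With equal failure rates of 12.5%, the SAP and frozen estimates differ by at most 0.07 in the grid; at 25% in both arms, by at most 0.11 (−6.30 versus −6.41). With unequal rates the shift is roughly the difference in failure rates × the gap:
- Placebo 20%, LB-102 10%, half of failures for lack of efficacy: 0.10 × 3.50 = 0.35. Simulated: −8.97 versus −8.57, or 0.40 toward LB-102.
- Placebo 10%, LB-102 20%, none for lack of efficacy: 0.10 × 5.11 = 0.51. Simulated: −5.06 versus −5.67, or 0.61 against LB-102.

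Other runs at 20% versus 10% gave shifts down to about 0.15. The largest, about 0.6, is 0.6/8 = 7.5% of the planned difference.

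**The case against.** **The bullets describe the iteration.** The sentence that states the rule also says the imputation is iterative, and the bullets agree with the code. So this is not a coding slip, and nothing in the rule says that one draw must be held flat to Week 4. That is one way to implement it. If the rule means the patient's own worst score, the code often imputes too low: by about 2 to 7 points when Week 4 alone is missing and half or more of failures are for lack of efficacy. This stands, but it leaves the conflict in place. Bullets and code together depart from Table 1 and the protocol, and SAP section 8 does not list the departure.

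**Early-termination scores.** PANSS is requested at early termination (protocol 5.3 and 7.2.14). SAP 5.2.4 maps it to the nearest window (Days 2 to 11 to the Day 8 visit, Days 25 to 30 to Day 28) and uses it when the planned visit did not occur. That shrinks the group first missing at Week 1, and the simulations in the working ignore it. In a separate run at correlation 0.8 with near-equal failure rates, complete early-termination data cut the gap from 3.7 to 3.0 points. It is reduced, not removed.

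**The frozen version has its own oddity.** In the table by last observed visit, the earliest leavers get the mildest penalty (+1.4 against +8.8). A sponsor could prefer the running maximum for that reason, but the documents would then have to say so.

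**Sensitivity analyses.** Analysis #3 avoids the chain by replacing the whole method with imputation from placebo. Analysis #1 keeps the same missing-data strategy, and #2 shifts only MAR-imputed values. None varies the horizon.

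**Conclusion.** The stated rule and the prescribed algorithm conflict, and this can be seen without simulation. As coded, the primary analysis gives early failures a higher Week 4 score on average than a horizon frozen at withdrawal would. The effect on the contrast is modest. All sizes rest on assumed sample size, failure rates and correlations.

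Three stronger readings are tempting and are not supported:
- *That the score at withdrawal no longer matters.* Observed scores remain predictors in the WORST4 step. Among failures last seen at Week 1, imputed Week 4 change still correlated 0.26 to 0.40 with observed Week 1 change. The dependence is diluted, not lost.
- *That every failure's trajectory climbs.* The rise is an average. Predictive mean matching can draw a lower donor, and the gap is near zero for lack-of-efficacy drop-outs first missing at Weeks 2 to 3 when improvement is strong and correlation high.
- *That the trial is tilted toward LB-102.* The direction depends on which arm has more failures, which the documents cannot tell us.

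**What to change.** Make the algorithm in SAP 5.11.2 match the rule. After early-termination scores are mapped, let Week j be a failure's first missing visit. Draw WORSTj once, set Weeks j to 4 to that value, and keep the patient out of later donor sets. The exclusion is needed because the code takes as a donor anyone with a score at that visit, and the carried values would otherwise qualify.

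If the sponsor intends the running maximum, reword Table 1 and the sentence in 5.11.2, list the change from the protocol in section 8, and report the frozen-horizon version as a sensitivity analysis.

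Either route costs some SAP wording and at most a few lines of code, with no new data. Under the first, the estimate may move by up to about half a point in either direction, so the choice should be made before unblinding.

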* Set Week 4 = WORST4 for missing data;

data step5b;
set step5a;
week_4 = ifn(missing(week_4), worst4, week_4);
run;

```

Upon completion of the above imputation steps, the change from baseline in the PANSS score will be derived and used in the statistical modelling. To such aim, a MMRM will be fit for each imputed dataset, including pooled study site, visit, treatment and treatment by visit interaction as categorical effects and Baseline PANSS total score as continuous covariate and the change from Baseline in the PANSS total score at 1, 2, 3 and 4 weeks after baseline as response. Correlation between repeated observations within a patient will be accounted for via an unstructured correlation matrix, however, should this structure lead to convergence issues, the following decreasingly complex alternative structures will be fit in turn until the model converges: Toeplitz, first-order autoregressive, and compound symmetry. The assessment of model convergence will be done prior to unblinding. The LS means for change from Baseline to all post-Baseline timepoints in the PANSS total score and their differences between the active treatment arms (50 and 75 mg) and placebo will be estimated for each imputed dataset. Model assumptions will be examined graphically for a random selection of 10% imputations (i.e. 10) via inspection of conditional residuals scatterplots (residuals vs predicted values), quantile-quantile plots and histograms. Should any substantial violation be observed, non-parametric analyses (e.g. Wilcoxon rank-sum test) will be adopted, and this decision will be documented based on blinded data prior to database lock. This model will be fit using the example SAS code below:

```

ods output estimates = est LMeans = lsm diff = diff;
proc mixed data =  plots (only) = studentpanel(marginal);
by _imputation_;
class subjid trt01pn avisitn siteid;
model chg = trt01pn siteid avisitn trt01pn*avisitn base / ddfm = kr;
repeated avisitn / type = un subject = subjid;
lsmeans trt01pn*avisitn / diff cl;
run;

```

The model estimates (LS means and their differences between treatment arms) will be pooled using Rubin's combination rules to incorporate the between-imputation with the within-imputation variability and to obtain one single point and interval treatment effect estimate for each active arm using the PROC MIANALYZE procedure. The below sample SAS code implements the pooling across imputations:

```

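### SAP 5.11.2: as described, the worst-value (MNAR) imputation for lack-of-efficacy and drug-related-AE dropouts replaces nothing, so the primary analysis would be MAR for every dropout

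*SAP*

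**What the plan says.** The rule is set by reason for discontinuation. Section 5.11.2 says that "missing data due to a discontinuation related to either lack of efficacy or drug-related AEs will be imputed assuming a MNAR mechanism", while "missing data due to discontinuation for any other reason or non-monotone missing data will be imputed under a MAR mechanism". Table 1 in Section 2.3 says the same.

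For the MAR part, Section 5.11.2 states: "This imputation will be performed using the following SAS code". That `PROC MI` runs by treatment arm over baseline and Weeks 1 to 4 and writes its result to `impute01` ("seed = 99 out = impute01 minimum").

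The worst-value part follows as a chain of steps building WORST1 to WORST4. The SAP describes what enters the chain: "with the input dataset of the first DATA STEP being the output dataset of the PROC MI step above". On the contents of that file, it speaks of it as "including the patient ID and the MAR-imputed PANSS data in wide format". The first step reads a different name, "set analysis02". Each week ends with a replacement of the form "week_4 = ifn(missing(week_4), worst4, week_4", so the worst value is used only if the score is still missing.

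**The concern.** A fully conditional `PROC MI` with no selection by reason leaves no missing PANSS score in its output. If that output goes into the worst-value chain, the chain has nothing to act on. Patients who left for lack of efficacy or a drug-related AE then keep the scores MAR gave them, which resemble those of patients who stayed in their arm. The prose wants them to follow the distribution of worst scores.

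This is the confirmatory analysis of the primary endpoint. The remapped early-termination sensitivity analysis (Section 5.11.3.1) repeats it, and the tipping-point analysis (Section 5.11.3.2) takes its set of shifted values from it, so both inherit the fault.

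**Working it through.** **Trace of the stated flow**

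1. MAR step: all five time points, by arm, with no `where` clause and no reason variable. Every missing score is filled.
2. Hand-off: the SAP text names this output as the input to the first DATA step. The contents it lists include no discontinuation reason and no flag for originally missing scores.
3. Worst-value steps: eight conditions, four `if not missing(week_k)` and four `ifn(missing(week_k), ...)`. None refers to reason.
4. Reset: none in text or code. `analysis02` is never created. As `impute01` is produced by arm and the WORST1 step runs by imputation, `analysis02` could simply be a sorted copy.

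So at week k no score is missing, all four replacements are idle, and the data leave the chain unchanged.

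The other reading is that these patients are held out of the MAR step. They are then absent from its output: in one simulated trial it held 291 of 324 patients and no missing scores. Some unwritten step is needed either way.

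**Emulation of the printed logic** (predictive mean matching with k = 5; 108 per arm in three arms; 25% dropout, of which 30% or 50% for the MNAR reasons; all assumed). Over 540 imputed datasets the flow as written made 0 replacements. With a reset added, 59 to 89 scores per dataset (23 to 35 patients) were replaced. Mean imputed Week 4 change in those patients moved from about −16 to −18 (improvement) to about +6.5 to +6.8 (worsening).

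Shift in the Week 4 active-minus-placebo difference, as written minus with reset (negative = too favourable to LB-102):
- 30% of dropouts MNAR-type in every arm: −8.04 − (−7.59) = −0.45
- 50% placebo, 30% active: −8.47 − (−9.04) = +0.57
- 30% placebo, 50% active: −8.18 − (−6.35) = −1.83

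**Wider simulation**

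Arm size is redacted, so the stated power of at least 85% cannot be verified directly. With the Section 3 inputs (difference 8, SD 18, 25% dropout, Hochberg), the chance that at least one dose passes is 83.7% at 100 per arm and 85.6% at 105, so arms of 105/105/105/35 were used.

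Assumptions:
- True difference 8 and Week 4 SD 18.
- MNAR-type dropout in 5 to 15% of each arm; lack of efficacy is 20–80% of it on active and 50–90% on placebo, skewed to poor responders.
- Drug-related-AE and other dropout at random.
- 0 or 50% of dropouts with an early-termination score kept as observed; 2% intermittent gaps.
- 10 imputations, and a Week 4 ANCOVA in place of the MMRM.

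There were 42 cases of 300 paired trials each, with Monte Carlo SE 0.02 to 0.06 points.

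| MNAR-type dropout, active / placebo | Shift in difference (points) | Change in chance that at least one dose passes (percentage points) |
|---|---|---|
| 15% / 5% | −2.8 to −1.9 | +18 to +35 |
| 12% / 7% | −1.9 to −1.2 | +12 to +23 |
| equal, at 5, 10 or 15% | −1.4 to −0.3 | 0 to +13 |
| 7% / 12% | −0.2 to 0.0 | −1 to +1 |
| 5% / 15% | +0.4 to +0.8 | −5 to −3 |

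In these cases the rule as intended replaces 31 to 132 scores per dataset, against 0 as written.

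The shift is close to pP × gP − pA × gA, where p is the share of MNAR-type dropouts (P placebo, A active) and g the mean worst-value score minus the MAR score (7 to 13 on placebo, 15 to 23 on active). At mid-range values:
- 15% / 5%: 0.05 × 10 − 0.15 × 19 = −2.35
- equal 10%: 0.10 × 10 − 0.10 × 19 = −0.90
- 5% / 15%: 0.15 × 10 − 0.05 × 19 = +0.55

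A further repeat gave about −3 to −0.7 when such dropout was equal or heavier on active, and +0.5 to +1.5 when heavier on placebo.

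**Smaller faults in the same code.** The WORST3 and WORST4 `PROC MI` calls lack the BY statement that WORST1 and WORST2 have, and the Week 4 MAR model omits `week_2`. In emulation (not a SAS run) these moved the difference by at most 0.03 and 0.02 points, within Monte Carlo error.

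**The case against.** The prose leaves no doubt about intent. The schematic in Section 5.11.2 separates patients whose Week 1 score was filled by MAR from those whose score is still missing, so it expects the MNAR dropouts to reach the chain unfilled. The worst-value code is labelled as sample code. The change of name from `impute01` to `analysis02` is compatible with an unprinted step. The listed contents are not exhaustive: they omit even the imputation index, so a reason variable may be present. Section 10 plans independent programming of the primary table, and a chain that replaced nothing would plainly breach the prose.

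Much of this stands. It shows that the correct analysis is recoverable, and that nobody can say from the documents that the final analysis will be MAR. The two completions that comply with the prose (reset after MAR, or hold out and add back) differ by only −0.02 to +0.06 points, so no real analysis choice is open.

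It does not remove the fault. The hand-off is in the SAP's own sentence, not only in the code, and both programmers would work from it. Section 5.11.5.5 shows the contrast: for the response endpoint it takes the MAR data and then overrides these dropouts by reason. Section 5.11.2 has no such step.

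The objection on size also stands in part. The largest shifts need more MNAR-type dropout on active than on placebo. If lack-of-efficacy withdrawals are mainly on placebo, the error works against LB-102. The pass probabilities assume a true effect of 8, and type I error was not computed.

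**Conclusion.** The concern holds. Followed as written, Section 5.11.2 applies the worst-value rule to no score, contrary to its own text and to Table 1. This follows from the text and code alone, with no assumption about dropout.

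The effect on the result is conditional on `analysis02` being the MAR output, and on a mix of dropout reasons that the documents do not give. Its size and sign are therefore illustrative: from about −3 to +1.5 points across the simulations, beside a design difference of 8. In the most unfavourable mix, 15% on active and 5% on placebo, the chance that at least one dose passes Hochberg rises from 56–75% to 91–93%. With equal shares the rise is 0 to 13 percentage points. Because this is the primary test, the text and code must be corrected before they are used.

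**What to change.** 1. Define `analysis02` in Section 5.11.2 as the MAR output in which, within each imputation, only the MAR-imputed post-withdrawal PANSS scores of patients who discontinued for lack of efficacy or a drug-related AE are set back to missing. Key this to the discontinuation reason and a missingness flag made before imputation. Keep all observed scores and the MAR fills for intermittent gaps.
2. Add a check that the number of reset scores is the same in all 100 imputations and equals the count of such scores in the unimputed data.
3. Add the BY-imputation statement to the WORST3 and WORST4 `PROC MI` calls, and restore `week_2` in the Week 4 MAR model.
4. In Section 5.11.3.2, make the tipping-point code shift only the scores that remain MAR-imputed after step 1. The prose already defines that set.

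The cost is SAP wording and a few lines of code, with no new data and no protocol amendment. If the database is already locked, SAP Section 5 provides for a post-lock addendum.

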### 3 SAMPLE SIZE

[REDACTED] patients will be randomized in a 3:3:3:1 ratio to placebo, LB-102 50 mg QD, LB-102 75 mg QD, or LB-102 100 mg QD, respectively, with [REDACTED] patients randomized to each of the first 3 arms and [REDACTED] to the last one (LB-102 100 mg). This will ensure at least 85% power at a 2-sided 5% significance level to detect a treatment difference on the primary endpoint of 8 between either LB-102 50 mg or 75 mg and placebo QD, assuming a common SD of 18, an overall drop-out rate of 25% and a Hochberg procedure to adjust for multiplicity. The sample size was estimated via Monte Carlo simulations using 10,000 simulated trials.

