## **5.11 Efficacy Analyses**

Statistical tests will be performed using a two-tailed 5% overall significance level, unless otherwise stated. For the primary analysis of the primary endpoint, a multiplicity strategy will be in place to ensure that the familywise error rate (FWER) is controlled at this level across the doses tested (see Section 5.11.7 for details).

All comparisons between treatments will be reported with 95% confidence intervals for the difference.

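### The MMRM fallback covariance structures assume equal variance at Weeks 1 to 4; if one is used and variance rises by Week 4, the Week 4 standard error is too small

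*SAP*

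**What the plan says.** SAP 5.11.2 fits the MMRM to each imputed dataset, with change in PANSS total at Weeks 1, 2, 3 and 4 as the response. The first choice is an unstructured covariance (type = un), which gives each visit its own variance. If that fails to converge, "the following decreasingly complex alternative structures will be fit in turn until the model converges: Toeplitz, first-order autoregressive, and compound symmetry". The section names no heterogeneous-variance version of these structures and no robust standard error. The sample code uses ddfm = kr, that is, model-based inference with the Kenward-Roger adjustment. Convergence is to be judged before unblinding.

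Protocol 10.4.4.2 is less specific. It allows the unstructured matrix "or the best fit structure should an unstructured matrix cause convergence issues", which does not limit the choice to equal-variance structures.

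On error rates, SAP 5.11 says "Statistical tests will be performed using a two-tailed 5% overall significance level", with Hochberg over the 50 mg and 75 mg doses (5.11.7). On variability, SAP section 3 gives one figure only, "assuming a common SD of 18". Neither document gives an SD by visit.

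The same MMRM is used elsewhere. Subgroup models (SAP 5.11.4.1) and Marder factor models (5.11.5.4) have no imputation. The PANSS positive subscale (5.11.5.2) includes the imputation step in the SAP, although protocol 10.4.4.3 says that the continuous secondary endpoints are analysed without imputation.

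**The concern.** The confirmatory contrast is at Week 4. Under Toeplitz, AR(1) or compound symmetry, its standard error comes from one variance shared by all four visits. If the true Week 4 variance is larger than the Weeks 1 to 4 average, that standard error is too small, the interval is too narrow, and the test rejects too often. Kenward-Roger does not repair this: it allows for uncertainty in estimating the assumed covariance, not for the wrong covariance.

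Three features of the design make a rise plausible:

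- The response is change from baseline, which is zero at baseline by construction.
- Entry restricts baseline PANSS to 80 to 120.
- Worst-value imputation for dropouts due to lack of efficacy or drug-related AEs accumulates by visit and mixes poor scores with those of improving patients. As an assumed illustration, moving 10% of patients by 20 points adds 0.1 × 0.9 × 20² = 36 to a variance of 18² = 324, so the SD goes from 18 to √360 ≈ 19.0.

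These are reasons to expect a rise, not a statement in the plan that there is one.

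**Working it through.** **The plan's own figure.** SAP section 3 states: "This will ensure at least 85% power at a 2-sided 5% significance level", for a difference of 8, SD 18, 25% dropout and Hochberg. The arm sizes are redacted, so this cannot be reproduced. Solving for n instead, 85% power to win on at least one dose when both doses work needs about 77 evaluable patients per main arm, or 77 / 0.75 ≈ 103 randomised. Other readings of the power statement give 130 to 150 randomised per main arm. The simulation below assumes 103/103/103/34.

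**Inputs.** Week 4 SD 18 (from the plan). SDs at Weeks 1 to 3 are assumed, with every profile ending at 18. Two-sided 5% per comparison, z = 1.96.

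**Step 1: one variance for all visits, no imputation.** With complete data and a treatment-by-visit term, the Week 4 estimate hardly depends on the covariance structure; its standard error does.

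- SE ratio ≈ √(mean of the four visit variances) / 18
- actual alpha = 2 × (1 − Φ(1.96 × ratio))

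| Assumed SDs, Weeks 1–4 | Mean variance | SE ratio | Actual alpha |
|---|---|---|---|
| 10/13/16/18 | (100+169+256+324)/4 = 212.25 | 14.57/18 = 0.809 | 11.3% |
| 14/16/17/18 | (196+256+289+324)/4 = 266.25 | 16.32/18 = 0.907 | 7.6% |
| 18/18/18/18 | 324 | 1.000 | 5.0% |
| 22/20/19/18 | (484+400+361+324)/4 = 392.25 | 19.81/18 = 1.100 | 3.1% |

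Fitting each of the three structures by likelihood to these covariances gave nearly the same answers: 11.3%, 7.6% to 7.8%, 5.0%, and 3.0% to 3.1%. So it makes little difference which of the three is reached.

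**Step 2: with imputation and Rubin pooling.** The pooled variance is W + (1 + 1/m)B. Only the within-imputation part W uses the averaged variance; the between-imputation part B does not, so the error is diluted. There were 1,500 null trials per profile, with about 26% MAR dropout, 20 imputations by regression within arm, and a correlation of 0.8 between adjacent visits. The Monte Carlo standard error near 5% is √(0.05 × 0.95 / 1500) ≈ 0.6 percentage points.

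| Assumed SDs | Mean SE, one variance | Mean SE, own Week 4 variance | Empirical SD | Alpha, one variance | Hochberg FWER, one variance | Alpha, own Week 4 variance |
|---|---|---|---|---|---|---|
| 10/13/16/18 | 2.38 | 2.82 | 2.76 | 9.1% | 10.5% | 5.3% |
| 14/16/17/18 | 2.59 | 2.81 | 2.69 | 6.4% | 5.9% | 4.3% |
| 18 throughout | 2.80 | 2.81 | 2.74 | 5.1% | 4.3% | 4.7% |
| 22/20/19/18 | 3.02 | 2.81 | 2.72 | 3.0% | 2.4% | 4.1% |

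In the steepest case the SE ratio moves from 0.809 without imputation to 2.38/2.82 = 0.844 with it. A Week 4-specific variance kept alpha at 4.1% to 5.3% in all four profiles.

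**Limits of step 2.** It used normal regression imputation under MAR, not the SAP's predictive mean matching followed by worst-value steps, and it left out site effects.

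**Step 3: how likely is a fallback?** The primary model is fitted to completed data with 4 visits, so the unstructured matrix has 4 × 5 / 2 = 10 parameters. Failure there is unlikely. It is more plausible in the BMI and baseline-PANSS strata, which are unimputed and smaller, still carry four arms (one with a tenth of the patients) and include site terms. The unimputed Marder factor models come next.

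**The case against.** The strongest reply is that the direction of the error is assumed. The documents give one common SD of 18 and no visit profile. With flat SDs nothing goes wrong, and with falling SDs the test is conservative. This stands: a reader might infer that the listed fallbacks always understate the standard error and inflate type I error, and the documents do not support that.

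The second reply is that the trigger and the harm sit in different places. Where type I error is controlled, in the primary test, non-convergence is unlikely. Where it is more plausible, the p-values are descriptive: formal testing is for the primary endpoint only, and both the secondary and the subgroup p-values are labelled descriptive. This also stands, and it is why the point is low priority. What remains is that the subgroup intervals are still reported and go into a forest plot.

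Third, the SAP has safeguards, but they do not meet the point. Judging convergence before unblinding prevents a choice driven by results; it does not correct a wrong variance. The residual plots are against predicted values, not by visit, and the stated remedy is a rank-based analysis rather than another covariance.

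A reader might also take the protocol to share the defect. It does not: its best-fit wording would allow a heterogeneous structure. It is the SAP that narrows this to the first listed structure that converges.

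**Conclusion.** The point holds as a conditional one. The three named fallbacks assume equal variance across Weeks 1 to 4 and are paired with model-based standard errors. If one is used and variance rises by Week 4, the Week 4 standard error is too small. With assumed SDs from 14/16/17/18 to 10/13/16/18, alpha at nominal 5% is about 7.6% to 11.3% without imputation and about 6.4% to 9.1% with it. The second range is the one closer to the planned primary test, and its lower end is a modest excess given the simulation error. The first range belongs to models fitted without imputation and should not be read as the error rate of the primary analysis. All of these figures rest on assumed SDs for Weeks 1 to 3.

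It does not follow that the primary result is at material risk: the unstructured model will probably converge on the imputed data, and then none of this arises.

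**What to change.** In SAP 5.11.2, place the heterogeneous-variance structures ahead of the current list: heterogeneous Toeplitz (TOEPH), then heterogeneous AR(1) (ARH(1)), then heterogeneous compound symmetry (CSH). Keep an equal-variance structure only as the last resort, and require a robust (sandwich) standard error whenever it is used. State that the same order applies to the subgroup and secondary-endpoint models.

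The heterogeneous structures should precede the present list rather than replace it outright. With four visits TOEPH has 7 covariance parameters and ARH(1) and CSH have 5 each, against 4, 2 and 2 for the current three. In a small stratum the larger structures may also fail, and the rule must still end somewhere.

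The cost is a few words in the SAP and the code, a few more covariance parameters if a fallback is reached, and a different degrees-of-freedom method in place of Kenward-Roger if the sandwich standard error is used. If the unstructured model converges, nothing changes.
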